5.3 Selection and timing of doses

Overall, MR levodopa strength will be 50, 100 or 150 mg, carbidopa strength will be 12.5, 25 or 65 mg and ODM-104 strength will be 0, 50 mg or 100 mg. Sinemet contains 100 mg of IR levodopa and 25 mg of carbidopa.

The strength of levodopa, carbidopa and ODM-104 will depend on the parallel group (Groups 1-4) the study subject has been assigned to. The doses during the 4 treatment periods are presented in [Table 1](#) in section [3.2](#).

In all parallel groups, depending on the treatment period, carbidopa with or without ODM-104 will be taken 4 times a day during the days 1-6. On day 7 (PK sampling day), carbidopa with or without ODM-104 will be taken at the same time with levodopa 4 times a day. The duration of treatment will be 7 days for carbidopa and ODM-104 and 1 day for levodopa. In one of the periods in Group 4, Sinemet will be taken on day 7 without ODM-104 and on days 1-6, only carbidopa 25 mg will be administered.

The selected strengths and dosing regimens are based on previous PK studies in healthy subjects conducted during ODM-104 development program and other levodopa programs.

Carbidopa and ODM-104 (in treatment periods including ODM-104) will be taken 4 times a day – first dose, 3.5 h, 7 h and 10.5 h doses, for 6 days. The study treatments should be taken

at the same time every day to provide even concentrations of the active ingredients. The recommended study treatment intake times on days 1-6 are 8:00, 11:30, 15:00 and 18:30 h.

Subjects will arrive at the study centre in the evening before day 1 (day -1) and stay at the study centre until the 24 h PK blood sample has been drawn in the morning of day 8. Subjects will take all study treatments at the study centre.

In the evening of day 6, subjects will start fasting for at least 10 h (from around 22:00 h on day 6) before the first morning dose (0 h) at approximately 8:00 h on day 7. Drinking of water is permitted until 1 h before dosing.

The recommended study treatment intake times on day 7 are the same as those on the previous 6 days: 8:00, 11:30, 15:00 and 18:30 h. Study treatments will be ingested with 200 ml of water. Study subjects should maintain an upright position (sitting or standing) for at least 1 h after the study treatment administration and as much as possible during the day until 24:00 h.

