6.4.1.2 Assessment of adverse events

All AEs must be elicited, documented and reported by the investigator to the sponsor from the time that a study subject signs the IC form until the end-of-study visit, i.e. 4-21 days after the last dose of study treatment.

SAEs and other significant AEs should be followed up until resolved or until the event is considered a chronic or stable outcome, or both.

AE may be notified to the investigator by the study subject or observed by the investigator clinically, or be an adverse change in laboratory assessment results. The investigator will

evaluate the subject's AEs at each visit by asking a standard question such as "Since you were last asked, have you felt unwell or different from the usual in any way?"

The investigator will assess and record the causality and severity of the AEs. Causality should be assessed in relation to the investigational medicinal product (see criteria for causality and severity below).

Causality criteria:

Related: The temporal relationship of the AE/SAE onset to the administration of the investigational medicinal product makes a causal relationship possible, and other drugs, therapeutic interventions or underlying conditions do not provide a sufficient explanation for the AE/SAE.

Not related: The temporal relationship of the AE/SAE onset to the administration of the investigational medicinal product makes a causal relationship unlikely, or other drugs, therapeutic interventions or underlying conditions provide a sufficient explanation for the AE/SAE.

Severity criteria:

Mild: Discomfort noticed, but it does not affect normal activity.

Moderate: Discomfort sufficient to reduce or affect normal daily activity.

Severe: Incapacitating with inability to work or perform normal daily activity.

From the time that a study subject candidate signs the IC form, newly appearing diagnosed diseases will be recorded on the AE eCRF.

Investigators must report all AEs to the sponsor on a specific AE eCRF irrespective of their assessment of the causal relationship of the investigational medicinal product to the event.

SAEs are by definition AEs and should be elicited in the same way, and also reported on the AE eCRF.

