6.4.1.4 Reporting of serious adverse events to competent authorities and ethics committees

The sponsor is responsible for expediting all suspected unexpected serious adverse reactions (SUSARs) as well as other safety issues requiring expedited reporting to the relevant authorities within applicable timelines.

Notification of the ECs about all relevant events (SUSARs, other relevant safety information) will be performed by the CRO as a delegate of the sponsor.

The expectedness evaluation is required for regulatory reporting and it is performed by the sponsor. The expectedness in this study is evaluated against the Reference safety information section in the current ODM-104 Investigator's brochure (days 1-7, groups 1-4) and the Sinemet UK Summary of Product Characteristics (SmPC) (day 7, group 4).

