#### **8.5.1 Adverse events**

Adverse events (AEs) reported after administration of the study treatment will be classified by System organ classes (SOC) and preferred terms using the MedDRA dictionary.

The number and proportion (%) of subjects having each AE will be given by treatment group. The numbers will be additionally broken down by severity (mild, moderate, severe) and by the causality (related, not related).

All serious adverse events (SAEs) and other significant AEs will be evaluated case by case. Additionally, narrative descriptions will be included in the study report for all SAEs and certain other significant AEs.

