| Formulation D1                    | XXXXX.XXX                    | X.XXXX | (XXXXX.XX , XXXXX.XX)      | <.XXXX  |
| Differences in Least Square Means |                              |        |                            |         |
| Formulation A1 B1                 | X.XXXXXXX                    | X.XXXX | ( X.XXXX , X.XXXX)         | X.XXXX  |
| Formulation A1 C1                 | X.XXXXXXX                    | X.XXXX | ( X.XXXX , X.XXXX)         | X.XXXX  |
| Formulation A1 D1                 | X.XXXXXXX                    | X.XXXX | ( X.XXXX , X.XXXX)         | X.XXXX  |
| Formulation B1 C1                 | X.XXXXXXX                    | X.XXXX | ( X.XXXX , X.XXXX)         | X.XXXX  |
| Formulation B1 D1                 | X.XXXXXXX                    | X.XXXX | ( X.XXXX , X.XXXX)         | X.XXXX  |
| Formulation C1 D1                 | X.XXXXXXX                    | X.XXXX | ( X.XXXX , X.XXXX)         | X.XXXX  |

Program: T\_14\_2\_1\_3\_2\_Levodopa statistical analysis for AUC0-24.sas

Date: 23MAY17:08:40

STUDY 3112005

DRAFT

Page: 1 (5)

Table 14.3.1.1 Summary of adverse events during study treatment (subject and event count)  
Safety population

|               |  | A1
(N=XX)
n (%) | B1
(N=XX)
n (%) | C1
(N=XX)
n (%) | D1
(N=XX)
n (%) |
|---------------|--|-----------------------|-----------------------|-----------------------|-----------------------|
| Subject count | AEs  | X (XX.X)              | X (XX.X)              | X (XX.X)              | X (XX.X)              |
|               | Related AEs                                | X (XX.X)              | X (XX.X)              | X (XX.X)              | X (XX.X)              |
|               | AEs leading to
discontinuation of study |                       |                       |                       |                       |
|               | Mild AEs                                   | X (XX.X)              | X (XX.X)              | X (XX.X)              | X (XX.X)              |
|               | Moderate AEs                               | X (XX.X)              | X (XX.X)              | X (XX.X)              | X (XX.X)              |
|               | Severe AEs                                 |                       |                       |                       |                       |
|               | SAEs                                       |                       |                       |                       |                       |

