| Event count   | AEs  | XX                    | XX                    | XX                    | XX                    |
|               | Related AEs                                | X                     | XX                    | XX                    | XX                    |
|               | AEs leading to
discontinuation of study |                       |                       |                       |                       |
|               | Mild AEs                                   | X                     | XX                    | X                     | XX                    |
|               | Moderate AEs                               | X                     | X                     | XX                    | X                     |
|               | Severe AEs                                 |                       |                       |                       |                       |
|               | SAEs                                       |                       |                       |                       |                       |

Program: T\_14\_3\_1\_1\_Summary of AEs.sas

Date: 23MAY17:08:57

STUDY 3112005

DRAFT

Page: 1 (10)

Table 14.3.1.2 Adverse events during study treatment (subject and event count)  
Safety population

| System Organ Class
Preferred Term                 | B1
(N=XX) |        | C1
(N=XX) |        | A1
(N=XX) |        | D1
(N=XX) |        |
|--|--------------|--------|--------------|--------|--------------|--------|--------------|--------|
|  | Subjects     | Events | Subjects     | Events | Subjects     | Events | Subjects     | Events |
|  | n (%)        | n      | n (%)        | n      | n (%)        | n      | n (%)        | n      |
| Cardiac disorders                                    |              |        |              |        |              |        |              |        |
| Total  | X ( X.X)     | X      | X ( X.X)     | X      |              |        |              |        |
| Cardiovascular insufficiency                         |              |        | X ( X.X)     | X      |              |        |              |        |
| Palpitations   | X ( X.X)     | X      |              |        |              |        |              |        |
| Gastrointestinal disorders                           |              |        |              |        |              |        |              |        |

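### The adverse-event tables are laid out by full-period treatment code only, so they cannot show whether events arose in the carbidopa/ODM-104 lead-in or after the one day of levodopa

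*SAP*

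**What the plan says.** Protocol 5.3 sets the exposure: "The duration of treatment will be 7 days for carbidopa and ODM-104 and 1 day for levodopa". For the Sinemet period it adds that "on days 1-6, only carbidopa 25 mg will be administered".

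SAP 8.5.1 plans the AE tabulation in two sentences: "The number and proportion (%) of subjects having each AE will be given by treatment group", and "The numbers will be additionally broken down by severity (mild, moderate, severe) and by the causality (related, not related"). The shells in SAP 10.3 follow this. "Table 14.3.1.1 Summary of adverse events during study treatment (subject and event count") and "Table 14.3.1.2 Adverse events during study treatment (subject and event count") each have one column per treatment code, and neither has a row or column for study day or for time relative to levodopa.

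The table list in SAP 10.1 (Tables 14.3.1.1 to 14.3.1.7) separates AEs before the start of study treatment, during treatment and at the end of study. Within a treatment period it offers only severity and causality. On causality, Protocol 6.4.1.2 says: "Causality should be assessed in relation to the investigational medicinal product".

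Day 7 is treated as distinct elsewhere. Protocol 6.4.1.4 limits one of the two expectedness references to the "Sinemet UK Summary of Product Characteristics (SmPC) (day 7, group 4"), and the ECG shell in SAP 10.3 reports day 6, day 7 before the first dose and day 7 after dosing on separate lines.

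**The concern.** A column headed with a combination code invites the reader to attribute its events to the whole combination, yet for six of the seven dosing days one component is absent. On the natural reading of the layout, an event on day 3 of period A4 is counted under Sinemet before any Sinemet was taken in that period. It also comes after a wash-out that Protocol 1.2.1 sets at four days or more.

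What is at stake is attribution. Protocol 1.2 says the study is to support the carbidopa and ODM-104 doses without formal phase II dose finding on clinical endpoints. Protocol 1.3 names gastrointestinal irritation as an important potential risk of ODM-104 and reports nausea and vomiting as relatively frequent in earlier PK studies. Protocol 1.2.2 sets a minimum body weight because levodopa concentrations bear on nausea. If a D column shows more gastrointestinal events than the matching A column, the two candidate explanations are the carbidopa/ODM-104 lead-in and the levodopa day. The planned tables cannot tell them apart.

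**Working it through.** The plan states no figure on this point to reproduce. The check sets out the exposure, what the planned breakdowns can separate, the lead-in regimens, and an illustration of the dilution.

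**1. Exposure (Protocol 5.3).** Four dosing times a day for 7 days gives 28 per period. Levodopa is taken at 4 of them: 4/28 = 1/7 = 14.3%.

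**2. Whether another planned breakdown supplies the split.**
- Before/during/end of study: no, because days 1-7 all fall within treatment.
- Severity: no.
- Causality: no. It is judged against the investigational product as a whole, so the related-AE row does not isolate levodopa.
- Listings 16.2.7.2 (AEs after start) and 16.2.6.1 (dosing times): these may allow case-by-case tracing, but they are not a summary.

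**3. Regimens on days 1-6.** Removing levodopa from the 16 codes in Protocol Table 1, at 14 men per group, leaves seven regimens:

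| Lead-in regimen | Codes | Planned n |
|---|---|---|
| Carbidopa 12.5 mg | A1 | 14 |
| Carbidopa 25 mg | A2, A4 | 28 |
| Carbidopa 37.5 mg | A3 | 14 |
| Carbidopa 65 mg | B1-B4 | 56 |
| Carbidopa 65 mg + ODM-104 50 mg | C1-C3 | 42 |
| Carbidopa 25 mg + ODM-104 100 mg | C4 | 14 |
| Carbidopa 65 mg + ODM-104 100 mg | D1-D4 | 56 |

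Check: 14 + 28 + 14 + 56 + 42 + 14 + 56 = 224 = 16 x 14.

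**4. Dilution of subject counts.** Let b be the daily probability of an AE on days 1-6, the same in both treatments compared, and p the probability on day 7, with days independent. Then P(any AE in period) = 1 - (1-b)^6 x (1-p), and a day-7 risk difference is multiplied by (1-b)^6. The documents give neither b nor p. Assuming p = 10% versus 40% (difference 0.30, ratio 4.0):

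| Assumed b per day | (1-b)^6 | Whole-period risks | Difference | Ratio |
|---|---|---|---|---|
| 1% | 0.94 | 15.3% v 43.5% | 0.28 | 2.85 |
| 2% | 0.89 | 20.3% v 46.8% | 0.27 | 2.31 |
| 5% | 0.74 | 33.8% v 55.9% | 0.22 | 1.65 |
| 10% | 0.53 | 52.2% v 68.1% | 0.16 | 1.31 |

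**5. Event counts.** Treating b and p as expected events per man, the expected count is 6b + p. With equal b, the difference stays at 14 x 0.30 = 4.2 events per 14 men. Only the ratio shrinks, to 2.88, 2.36, 1.75 and 1.43 for the four values of b.

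**6. A single preferred term.** Unrelated lead-in events do not enter a nausea or vomiting row, so the relevant rate is lower. If 2% of men had that term at any time on days 1-6, the ratio is (1 - 0.98 x 0.60)/(1 - 0.98 x 0.90) = 0.412/0.118 = 3.5. At 5% it is (1 - 0.95 x 0.60)/(1 - 0.95 x 0.90) = 0.430/0.145 = 3.0.

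**The case against.** The strongest reply is that nothing planned is harmed. The objectives are pharmacokinetic and AEs are summarised descriptively; no AE hypothesis, test or contrast is named. A reader might infer that the plan contains a tolerability comparison of levodopa strengths, or of MR levodopa with Sinemet, that this layout spoils. The documents do not support that, and this part of the reply stands in full.

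The design also limits such a reading whatever the layout. No man receives two MR levodopa strengths, so strengths are compared only across groups. B4, C4 and D4 differ from A4 in carbidopa, ODM-104 or both as well as in formulation. The contrast that changes formulation alone is A2 with A4, again across groups. A paired analysis of 14 men would fit neither.

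Nor are days 1-6 misplaced as such. The codes denote combinations, and those days carry most of the carbidopa and ODM-104 exposure. A man who stops on day 3 has received study treatment and belongs in the safety population. The full-period table is therefore valid for the combinations as given.

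A reader might also infer that splitting one lead-in regimen over four columns hides rare events. It does not: all four columns are reported and can be added. Pooling is a convenience.

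Finally, the shells are draft examples, and the rule assigning an AE to a code is inferred from their layout, because the SAP does not write one. That tempers the criticism but is itself a gap, most plainly for wash-out events. The expectedness rule in Protocol 6.4.1.4 concerns regulatory reporting; it shows that day 7 is recognised as different but does not prescribe a tabulation.

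None of this supplies the missing information on when, relative to levodopa, the events began.

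**Conclusion.** The point holds as a limitation of the descriptive safety tables and a cheap improvement to them. It is not an error in a planned comparison. The planned AE tables cannot separate lead-in events from events after levodopa, and the causality row does not repair this.

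Any levodopa reading of subject proportions or ratios is diluted, by an amount that cannot be estimated from the documents. The figures in the working rest on assumed rates, independent days and equal lead-in rates in the treatments compared. They show direction and range only, and the larger dilutions suit an any-AE row better than a single preferred term.

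Where the lead-in regimens are identical (B1/B2/B3, C1/C2/C3, D1/D2/D3, and A2 v A4), differences in expected event counts are not biased, only noisier. Where they differ, as in A v D within a group, the whole-period difference is a fair description of the combinations but mixes lead-in and levodopa-day effects.

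**What to change.** Keep the full-period tables as the overall summary. Then:

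1. In SAP 8.5.1, state how an AE is assigned to a treatment code, including AEs with onset in a wash-out, and make the rule consistent with Table 14.3.1.7 (AEs at the end of study).
2. Add a supplementary lead-in table: onset from the first dose on day 1 until just before the first levodopa dose on day 7. Tabulate by regimen actually taken, pooled across groups, using the seven regimens and planned numbers in the working.
3. Add a supplementary levodopa-phase table: onset from the first levodopa dose on day 7, ending where the rule in item 1 says. Tabulate by the 16 codes, with men given at least one levodopa dose in that period as the denominator.
4. Use onset times if they are recorded, otherwise onset date. With dates alone, events early on day 7 before dosing would fall in the levodopa phase; say so in a footnote.

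AEs are already recorded on each of days 1-7 (Protocol 6.1.2), so study conduct does not change. The cost is SAP wording, a phase variable in the AE programs, a few more table pages and small day-7 cells, which should be read descriptively.
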